### 9.1.6 Vital Sign Procedure

Vital signs to be measured are oral body temperature, sitting (after resting for 5 minutes) blood pressure, heart rate (beats per minute), and sitting respiratory rate. Heart rate and blood pressure will also be measured after 5 minutes supine and after 1 and 3 minutes standing, if possible. The investigator must document in the source document the reason for not obtaining a standing or supine blood pressure (eg, the subject is in a wheelchair).

Vital signs should be measured at the same time of day across visits, if possible. When vital signs are scheduled at the same time as blood draws, the blood draw will take priority and vital signs will be obtained within 0.25 hour before or after the scheduled blood draw, if possible.

All vital sign data collected at study visits will be recorded on the source documents and in the eCRF.

**9.1.7** CCI [REDACTED]

CCI [REDACTED]

**9.1.8 Documentation of Study Drug**

A dosing card will be provided to the subject and/or caregiver at each clinic visit to record daily AM and PM study drug administration throughout the study, including changes in dosing regimen (de-escalation) that may occur between visits and during the de-escalation period of the study.

**9.1.9 Documentation of Concomitant Medications**

Concomitant medication is any drug given in addition to the study drug. These may be prescribed by a physician or obtained by the subject over the counter. Concomitant medication is not provided by Takeda. At each study visit, subjects will be asked whether they have taken any medication other than the study drug (used from signing of informed consent through the end of the study), and all medication including vitamin supplements, over-the-counter medications, and oral herbal preparations, must be recorded in the source document and eCRF. Documentation will include generic medication name, dose, unit, frequency, route of administration, start and end dates, and reason for use.

**9.1.10 Documentation of Concurrent Medical Conditions**

Concurrent medical conditions are those significant ongoing conditions or diseases that are present at signing of informed consent. These include clinically significant laboratory, ECG, or physical examination abnormalities noted at Screening (Visit 1), according the judgment of the

investigator. The condition (ie, diagnosis) should be described and recorded on the Medical History form.

### 9.1.11 Procedures for Clinical Laboratory Samples

Blood and urine samples are to be collected at the time points stipulated in the Schedule of Study Procedures (Appendix A). Blood samples for hematology and serum chemistry tests are to be collected after an overnight fast of  $\geq 8$  hours, if possible. Samples will be collected in accordance with acceptable laboratory procedures. Details of these procedures and required safety monitoring will be given in the laboratory manual.

For an individual subject, the maximum volume of blood collected at any single visit will be approximately 71 mL, and the approximate total volume of blood collected over the course of the study will be 230 mL (Table 9.a).

**Table 9.a Approximate Blood Volume**

Sample Type	Sample Volume (mL)	Number of Samples (a)			Total Volume (mL)
		Screening Visit	Part 1	Part 2	
HIV, HBsAg, HCV (b)	6	1	---	---	6
HCV RNA detection by qPCR (c)	6	1	---	---	6
FSH (d)	(d)	1		1	(d)
Estradiol (e)	2	1		1	4
Serum chemistry (f)	6	1	1	2	24
Hematology	2	1	1	2	8
Plasma sample for TAK-935 PK analysis	4	---	8	3	44
Plasma sample for AED analysis	4	---	3	3	28
Plasma sample for PD analysis (g)	4	2	16	6	104
Blood sample for DNA PGx	6	---	1	---	6
Blood sample for RNA PGx (g)	2.5	---	2	2	10
Total Blood Volume (mL)					240

--- =not applicable.

(a) Does not include blood draws at any unscheduled visits.

(b) One 2-mL blood sample for each test.

(c) Subjects who are positive for hepatitis C Ab should return to the clinic for an unscheduled visit to provide a blood sample for HCV qPCR.

(d) For diagnostic purposes in female subjects only; sample will be run from serum chemistry volume (no extra volume required).

(e) In female subjects only.

(f) Includes serum pregnancy test for female subjects of childbearing potential.

(g) Two blood samples per scheduled time.

The clinical laboratory tests to be performed are listed in [Table 9.b](#).

**Table 9.b Clinical Laboratory Tests**

Hematology	Serum Chemistry	Urinalysis (a)	Study Specific
RBC	ALT	pH	Plasma
WBC with differential (% and absolute)	Albumin	Specific gravity	CCI
Hemoglobin	Alpha-1-acid glycoprotein	Protein	
Hematocrit	Alkaline phosphatase	Glucose	Plasma (Concomitant AEDs)
Platelets	AST	Blood	Carbamazepine
PT/INR	Total bilirubin	Nitrite	Clobazam
aPTT	Total protein		Valproic acid
	Creatinine	Microscopic Analysis: (b)	Phenytoin
	Blood urea nitrogen	RBC/high power field	Topiramate
	Creatine kinase	WBC/high power field	Lamotrigine
	GGT	Epithelial cells, casts etc	Rufinamide
	Potassium		Zonizamide
	Sodium		Phenobarbital
	Glucose		Levetiracetam
	Chloride		Lacosamide
	Bicarbonate		10-hydroxycabazepine (metabolite of oxcarbazepine)
	Calcium		Felbamate
	Total cholesterol		
	HDL cholesterol		
	LDL cholesterol		
	Triglycerides		
	FSH (c)		
	Estradiol (d)		

**Diagnostic Screening**

Serum

HIV  
 HBsAg and anti-HCV  
 HCV RNA detection by qPCR (e)  
 hCG (for pregnancy) (f)

Urine (a)

Drug screen including amphetamines, barbiturates,  
 benzodiazepines, cannabinoids, cocaine, opiates, alcohol, and  
 cotinine  
 hCG (for pregnancy) (f)

aPTT= activated partial thromboplastin time, FSH=follicle-stimulating hormone, GGT= $\gamma$ -glutamyl transferase,  
 HDL=high-density lipoprotein, LDL=low-density lipoprotein, PT=prothrombin time, RBC=red blood cell,  
 WBC=white blood cell.

(a) If urine cannot be collected at the time of the Screening Visit or other Visits due to the subject's cooperation or because the subject is wearing a diaper, it is acceptable for the subject to continue in the study and the reason should be documented in the source document.

(b) Only if dipstick results are positive.

(c) For diagnostic purposes in female subjects only.

(d) In female patients only

(e) Subjects who are positive for hepatitis C Ab should return to the clinic for an unscheduled visit to provide a blood sample for HCV qPCR.

(f) Only for female subjects of childbearing potential. If urine cannot be collected at Visit 2, the reason should be documented in the source document and the results of the serum pregnancy test obtained at Visit 1 must be confirmed to be negative by the investigator prior to randomization. An additional serum hCG pregnancy test will be performed at the Final Visit.

The central laboratory will perform laboratory tests for hematology, serum chemistry, and urinalysis. The results of clinical laboratory tests will be returned to the investigator, who is responsible for reviewing and filing these results. The investigator will maintain a copy of the laboratory accreditation and the reference ranges for the laboratory used.

If subjects experience ALT or AST  $>3 \times \text{ULN}$ , follow-up laboratory tests (at a minimum, serum alkaline phosphatase, ALT, AST, total bilirubin, GGT, and INR) should be performed preferably within 48 to 72 hours and no later than 5 days after the abnormality was noted.

(Please refer to Section 7.5 for discontinuation criteria and Section 10.2.3 for reporting requirements related to ALT or AST  $>3 \times \text{ULN}$  in conjunction with total bilirubin  $>2 \times \text{ULN}$ .)

If the ALT or AST remains elevated  $>3 \times \text{ULN}$  on these 2 consecutive occasions, the investigator must contact the Medical Monitor for consideration of additional testing, close monitoring, possible discontinuation of study drug, and discussion of the relevant subject details and possible alternative etiologies. The abnormality should be recorded as an AE (please refer to Section 10.2.3 for reporting requirements).

If urine cannot be collected due to the subject's cooperation or because the subject is wearing a diaper, the reason should be documented in the source document and, for female subjects, the results of the serum pregnancy test obtained at Visit 1 must be confirmed to be negative by the investigator prior to randomization.

### 9.1.12 Contraception and Pregnancy Avoidance Procedure

From signing of informed consent, throughout the duration of the study, and for up to 30 days after last dose of study drug, nonsterilized\*\* male subjects who are sexually active with a female partner of childbearing potential\* must use barrier contraception (eg, condom with spermicidal cream or jelly). In addition, they must be advised not to donate sperm during this period. Females of childbearing potential who are partners of male subjects are also advised to use additional contraception as shown in the list of adequate contraception below.

From signing of informed consent, throughout the duration of the study, and for 30 days after the last dose of study drug, female subjects of childbearing potential\* who are sexually active with a nonsterilized male partner\*\* must use adequate contraception. In addition, they must be advised not to donate ova during this period.

\*Females NOT of childbearing potential are defined as those who have been surgically sterilized (hysterectomy, bilateral oophorectomy, or tubal ligation) or who are postmenopausal (eg, defined as  $\geq 1$  year since last regular menses with an FSH  $>40$  IU/L or  $\geq 5$  years since last regular menses, confirmed before any study drug is administered).

\*\*Sterilized males should be  $\geq 1$  year postvasectomy and have confirmed that they have obtained documentation of the absence of sperm in the ejaculate.

An acceptable method of contraception is defined as one that has no higher than a 1% failure rate per year when used consistently and correctly. In this study, where medications and devices containing hormones are excluded, the only acceptable methods of contraception are as follows:

**CONFIDENTIAL**

**Barrier methods (each time the subject has intercourse):**

- Male condom PLUS spermicide.
- Cap (plus spermicidal cream or jelly) PLUS male condom and spermicide.
- Diaphragm (plus spermicidal cream or jelly) PLUS male condom and spermicide.

**Intrauterine devices:**

- Copper T PLUS condom or spermicide.

**Sterilization:**

- Bilateral tubal occlusion.
- Vasectomized partner (provided that the partner is the sole sexual partner of the study participant and the absence of sperm in the ejaculate has been confirmed).

**Abstinence:**

- Sexual abstinence, if it is the preferred and usual lifestyle of the subject, will be considered an acceptable method of contraception on a case-by-case basis upon prior approval by the Medical Monitor. Subjects practicing abstinence as a method of contraception must refrain from heterosexual intercourse throughout the duration of the study and for 30 days after last dose of study drug.

Subjects will be provided with information on acceptable methods of contraception as part of the subject informed consent process and will be asked to sign a consent form stating that they understand the requirements for avoidance of pregnancy, donation of ova, and sperm donation during the course of the study and for 30 days after the last dose of study drug. This may be signed by the legal representative of the subject.

All female subjects of childbearing potential must have a negative serum hCG pregnancy test at Screening (Visit 1) and a negative urine hCG pregnancy test on Day 1 (Visit 2), before receiving any dose of study drug. During the course of the study, subjects will receive continued guidance with respect to the avoidance of pregnancy and sperm donation as part of the study procedures. An additional serum hCG pregnancy test will be performed at the Final Visit.

**9.1.13 Pregnancy**

If any subject is found to be pregnant during the study, she should be withdrawn and any sponsor-supplied drug should be immediately discontinued. In addition, any pregnancies in the partner of a male subject during the study or for 30 days after the last dose should also be recorded following authorization from the subject's partner.

If the pregnancy occurs during administration of active study drug, for example, after Visit 2 or within 30 days of the last dose of active study drug, the pregnancy should be reported immediately, using a pregnancy notification form, to the contact listed in Section 1.1.

Should the pregnancy occur during or after administration of blinded study drug, the investigator must inform the subject of their right to receive treatment information. If the subject chooses to receive unblinded treatment information, the individual blind should be broken by the investigator. Subjects randomized to placebo need not be followed.

If the female subject and/or female partner of a male subject agrees to the primary care physician being informed, the investigator should notify the primary care physician that the subject/female partner of the subject was participating in a clinical study at the time she became pregnant and provide details of treatment the subject received (blinded or unblinded, as applicable).

All reported pregnancies, including those in female partners of male subjects, will be followed up to final outcome, using the pregnancy form. The outcome, including any premature termination, must be reported to the sponsor. An evaluation after the birth of the child will also be conducted.

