Subjects who are unwilling to continue into Part 2 of the study will proceed directly to the Final Visit (at Day 31), including dose de-escalation, as appropriate, followed by the 30-day Follow-up Period.

Part 2 of the study is designed to investigate the safety, tolerability, PK, and PD of TAK-935 in adult subjects with developmental and/or epileptic encephalopathies in an open-label manner. All subjects who complete the Double-Blind Treatment Period in Part 1 will have the option to continue directly into the Open-Label Treatment Period in Part 2. Because some subjects may enter Part 2 after receiving placebo and others TAK-935 up to 300 mg BID and to maintain the study blind, all subjects will start on TAK-935 200 mg BID at the start of Part 2. On Day 31 (Visit 5), subjects will return to the clinic and receive TAK-935 200 mg BID from Days 31 to 40 but may be reduced to 100 mg BID in subjects who cannot tolerate the 200 mg BID dose or demonstrate safety concerns, based on the investigator's judgment and in consultation with the subject's caregiver, when applicable. Subjects who cannot tolerate the 100 mg BID dose or demonstrate safety concerns, based on the investigator's judgment and in consultation with the subject's caregiver, will be discontinued from the study. On Day 41 (Visit 6), subjects will return to the clinic; at this visit, the investigator will review the subject's safety data and will discuss the benefit-risk with the subject or subject's legally acceptable representative before proceeding to

increase the dose from 200 mg BID to 300 mg BID, and this dose level will be maintained until the Final Visit (Visit 7) for the dose de-escalation phase. Subjects' dose may be increased or decreased before Day 41 (Visit 6) based on clinical condition (ie, increasing seizures) and investigator judgment. This dose may be reduced to 200 mg BID in subjects who cannot tolerate the 300 mg BID dose or demonstrate safety concerns, as described above. Subjects for whom the dose was reduced to a lower dose level will stay on that dose level until the Final Visit (Visit 7) for the dose de-escalation phase. Three days after each dose up-titration or de-escalation, subjects will be contacted by phone to monitor study drug compliance, concomitant medication use, and AEs. Any change in dose will be documented in the subject's clinic chart and the subject's caregiver will be advised to note the same in the dosing card.

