**Table 6.a Planned TAK-935 BID Doses and Associated Estimated EO Levels**

TAK-935 BID Dose (mg)	Average EO Level (%) (a)
300	85-95
200	80-90
100	70-80

(a) Average EO% at steady state during a dosing interval.

The investigator, in consultation with the sponsor, may decide to reduce the IP (TAK-935 or placebo) during Part 1 and TAK-935 during Part 2 dose at any time during the study, in the event of any safety or tolerability concerns. In Part 1, the planned starting dose of TAK-935 for adult subjects is 100 mg BID to achieve an average steady-state EO of approximately 70% to 80%. If well tolerated, this dose will be increased to 200 mg BID on Day 11 and subsequently to 300 mg BID on Day 21; the average steady-state EO at these doses are expected to be approximately 80% to 90% and 85% to 95%, respectively ([Table 6.a](#)).

In Part 2, the planned starting dose of TAK-935 for all subjects, including those who received placebo in Part 1, is 200 mg BID to be increased to 300 mg BID. The dose may be decreased at any time due to safety or tolerability concerns.

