#### **8.4 Unblinding Procedure**

The study drug blind in Part 1 shall not be broken by the investigator unless information concerning the study drug is necessary for the medical treatment of the subject. If possible, the sponsor/designee should be notified before the study drug blind is broken. If a medical emergency requiring unblinding occurs, the investigator (or designee) at the site will contact the sponsor or designee (see Takeda Medical Monitor contact information listed in Section 1.1) to assess the necessity to break the study drug blind.

For unblinding a subject, the investigator can obtain the study drug blind information by accessing the IVRS/IWRS. The sponsor/designee must be notified immediately if the study drug blind is broken. The date, time, and reason the blind was broken must be recorded in the source documents and on the appropriate eCRF.

If any site personnel is unblinded, study drug must be de-escalated in consultation with the Medical Monitor and the subject must be withdrawn from the study. The reason for withdrawal should be recorded as "Protocol Deviation." Subjects who are withdrawn early from the study should undergo all procedures scheduled for the Final Visit at the time of withdrawal.

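### The pregnancy follow-up waiver in Protocol 9.1.13 goes by randomised arm rather than drug taken, so it can be read to cover a TAK-935-exposed pregnancy

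*Protocol*

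**What the plan says.** Four statements in Protocol 9.1.13 bear on this point, in this order.

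- **Reporting trigger (second paragraph).** This is tied to drug actually taken. For a pregnancy during administration of active drug, or "within 30 days of the last dose of active study drug, the pregnancy should be reported immediately". The example given is a pregnancy after Visit 2.
- **Scope and unblinding (third paragraph).** It opens with "Should the pregnancy occur during or after administration of blinded study drug", obliges the investigator to tell the subject of the right to treatment information, and continues: "If the subject chooses to receive unblinded treatment information, the individual blind should be broken by the investigator".
- **Waiver (end of the third paragraph).** "Subjects randomized to placebo need not be followed".
- **General rule (last paragraph).** "All reported pregnancies, including those in female partners of male subjects, will be followed up to final outcome". It contains no exception for placebo.

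On treatment in Part 2, Protocol 6.1 says that all subjects who complete Part 1 "will have the option to continue directly into the Open-Label Treatment Period in Part 2". Protocol 6.2.2.2, in the text below Table 6.a, says that "the planned starting dose of TAK-935 for all subjects, including those who received placebo in Part 1, is 200 mg BID", to be raised to 300 mg BID.

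**The concern.** In a parallel-group trial without crossover, assigned arm and exposure would coincide (dispensing errors aside) and the waiver would do no harm. Here every placebo subject who continues moves to TAK-935, so the waiver uses the wrong criterion. Its paragraph also covers pregnancy after blinded drug, which does not exclude Part 2 or follow-up.

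A site that learns a pregnant subject was randomised to placebo could therefore take the sentence at its word and stop follow-up, although the pregnancy was exposed to TAK-935. The information at stake is the pregnancy and birth outcome. The SAE rules replace it only in part:

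- Birth defects (10.1.3), and spontaneous abortion, stillbirth and fetal death (Table 10.a), are SAEs.
- AE collection ends at the Follow-up Visit (10.2.1.1).
- A later SAE goes to the sponsor only if it is reported spontaneously to the investigator and considered related to study participation (10.2.2).

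**Working it through.** The plan gives no figure to reproduce. The check is a comparison of the texts by case, followed by day counts and expected numbers.

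**1. Cases for a subject randomised to placebo**

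| Case | TAK-935 exposure | Reporting rule (para 2) | Waiver by its words | General rule (last para) |
|---|---|---|---|---|
| Conceived and found in Part 1 | None | Not triggered by actual drug, but a blinded site may report | Applies | Applies if reported |
| Conceived in Part 1 on placebo, found in Part 2 | Yes, from Day 31 | Unclear: began on placebo, continued on active drug | Applies | Applies if reported |
| Conceived in Part 2 or within 30 days of last dose | Yes | Triggered | Applies | Applies |

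The waiver's wording fits all three rows, because its only condition is the assigned arm. In the last two rows it points the opposite way from follow-up of an exposed pregnancy. The middle row is the least settled, since even the reporting rule can be argued either way.

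**2. Could a Part 1 conception go unnoticed into Part 2?**

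Appendix A schedules a urine test before the first dose on Day 1 and then a serum test at the Final Visit (Day 85 for those in Part 2). It schedules none at Day 31. Footnote (i) allows extra tests at the investigator's discretion. Planned TAK-935 exposure before the Day 85 test is 84 − 31 + 1 = 54 days, which matches 10 days of titration plus 44 of maintenance (6.1). This is the longest planned case for a woman who conceives on placebo.

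**3. When would the birth fall?**

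Assumption: birth 35 to 40 weeks (245 to 280 days) after conception. For conception in Days 1 to 30:

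- Earliest: Day 1 + 245 = Day 246, and 246 − 121 = 125 days after the Follow-up Visit on Day 121.
- Latest: Day 30 + 280 = Day 310, and 310 − 121 = 189 days after it.

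A birth in this range falls after routine AE collection has closed.

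**4. How many such pregnancies?**

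Inputs: 4 planned placebo subjects (6.1), women or men through their partners; contraceptive failure of at most 1% per year with consistent and correct use (9.1.12). The whole placebo arm is used as a ceiling, before any replacements. The longer window runs to Day 120, that is, the last planned dose on Day 90 plus 30 days.

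Expected conceptions = subjects × annual failure rate × days / 365

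| Window | At 1% per year | At 10% per year (assumed) |
|---|---|---|
| Days 1 to 30 | 4 × 0.01 × 30/365 = 0.0033 | 0.033 |
| Days 1 to 120 | 4 × 0.01 × 120/365 = 0.0132 | 0.132 |

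The documents give neither the sex split nor the number who will continue into Part 2. Either would lower these figures.

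**The case against.** The strongest reply is that 9.1.13 can be read coherently. The reporting rule follows active drug, the last paragraph follows every reported pregnancy to outcome, and the waiver covers what remains, which is placebo exposure only. In Part 2 the drug is open-label (8.3), so a site would have to treat a patient it knows to be on TAK-935 as a placebo patient, and set aside two explicit instructions for a permissive one.

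That reading is sensible and probably intended, and it lowers the practical risk. It does not settle the matter, because the protocol never states it. A site still blinded may report at once, as the Visit 2 example suggests, and the pregnancy then counts as reported. If allocation later proves to be placebo, the waiver can have effect only by overriding the last paragraph, and its sole stated condition is the arm.

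A second reply is withdrawal. Section 8.4 says "The study drug blind in Part 1 shall not be broken by the investigator unless information concerning the study drug is necessary" for medical treatment, and requires withdrawal if site personnel are unblinded. Section 7.5 requires withdrawal of a pregnant subject. Together these should keep placebo subjects whose pregnancy is found in Part 1, and partner cases unblinded in Part 1, from going on to TAK-935. They do not help with pregnancies that begin or are first detected in Part 2.

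Third, item 25 of Appendix C promises regular pregnancy tests during the study, and clinic visits on Days 31 and 41 give chances to notice a pregnancy. Yet Appendix A schedules no test at those visits, so earlier detection depends on the investigator.

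The point about rarity stands in full.

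**Conclusion.** The concern holds. By its wording the waiver reaches TAK-935-exposed pregnancies in subjects randomised to placebo, and it conflicts with the general follow-up rule with no stated order of precedence. Harm requires three things: a pregnancy in or through one of about 4 planned subjects, a known allocation, and a site that relies on the waiver. The first alone has an expected count of at most about 0.003 (Days 1 to 30) to 0.013 (Days 1 to 120) at the protocol's contraception standard, or 0.03 to 0.13 at the assumed tenfold rate. No endpoint, analysis set or summary changes. The change should be made because a missed outcome in an exposed pregnancy may not be recoverable, and because correcting the rule costs almost nothing. Confidence is medium, since a protective reading is available and sites may well adopt it.

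**What to change.** Replace the waiver sentence in 9.1.13 with:

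> Pregnancies in subjects, or in partners of subjects, need not be followed where the subject received placebo only and took no TAK-935 before or during the pregnancy.

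State the same exception in the last paragraph, so that the waiver and the general rule agree. Alternatively, delete the waiver sentence and let the last paragraph apply to every reported pregnancy.

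The cost is protocol wording only: one sentence replaced and one exception added, or one sentence removed. No visit, test or analysis is added.
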